Appendix C. ECOG Performance Status Scale

With:

Appendix C. Serious Adverse Event Contingency Reporting Form

Section: Appendix C. Serious Adverse Event Contingency Reporting Form Insert new sample reporting form

Section: Appendix D. ECOG Performance Status Scale Section caption updated

Replace:

Appendix D. Pharmacy Guide

With:

Appendix D. ECOG Performance Status Scale

Section: Appendix E. Pharmacy Guide Section caption updated

Replace:

Appendix E. Pregnancy Notification Worksheet *With:*

Appendix E. Pharmacy Guide

Section: Appendix F. Pregnancy Notification Worksheet Section caption updated

Replace:

Appendix F. RECIST 1.1 With Modifications

With:

Appendix F. Pregnancy Notification Worksheet

Section: Appendix F. Pregnancy Notification Worksheet Updated worksheet

Section: Appendix G. Lactation Notification Worksheet New Section and sample worksheet *Add*:

Appendix G. Lactation Notification Worksheet

Section: Appendix H. RECIST 1.1 With Modifications New Section *Add*: Appendix H. RECIST 1.1 With Modifications

		9.6.4	Adverse Events and Disease-related Events	40
		9.6.5	Laboratory Test Results	41
		9.6.6	Vital Signs	42
		9.6.7	Physical Measurements	42
		9.6.8	Electrocardiogram	42
		9.6.9	Antibody Formation	42
		9.6.10	Exposure to Investigational Product	42
		9.6.11	Exposure to Other Protocol-specified Treatment	43
		9.6.12	Exposure to Concomitant Medication	43
10.	Chan	ges From	Protocol-specified Analyses	45
11.	Litera	ture Citati	ons / References	46
12.	Priorit	ization of	Analyses	47
13.	Data I	Not Cover	red by This Plan	48
14.	Apper	ndices		49
	Apper	ndix A. Te Procedu	echnical Detail and Supplemental Information Regarding Statisti Ires and Programs	cal 49
	Apper	ndix B. Co	oncomitant Medications	52

List of Table

Table 9-1.	Efficacy Endpoint Summary Table	25
Table 9-2.	Safety Endpoint Summary Table	30

List of Abbreviations and Definition of Terms

Abbreviation or Term	Definition/Explanation
AE	Adverse Event
ATE	Arterial thromboembolic event
Baseline Value	The baseline value is the value measured on study day 1 before the first dose of investigational product. If such a measurement is not available, the closest value measured within 7 days before randomization/ study day 1 will be used as the baseline value. For assessments not scheduled to be performed on study day 1, the baseline value is the value from the screening period measured closest to study day 1.
	The definition above will be used to derive "baseline" hemoglobin but it should be noted that the "screening" hemoglobin is the value taken just prior to randomization to determine eligibility and randomization stratum; and the "pre-chemotherapy" hemoglobin is the value taken just prior to the start of first line chemotherapy for NSCLC. It should also be noted that "baseline" in terms of imaging studies will be defined as the imaging studies performed just prior to the start of first line chemotherapy for NSCLC.
CIA	Chemotherapy-induced anemia
CTCAE	Common Toxicity Criteria for Adverse Events
DMC	Data monitoring committee
ECOG	Eastern Cooperative Oncology Group
eCRF	Electronic case report form
EDC	Electronic data capture
End of the Efficacy Treatment Period	End of the efficacy treatment period is defined as 21 days after either the last dose of IP or the last dose of chemotherapy, whichever is later; the EOETP will be set to the EOTP if the EOETP exceeds the EOTP
End of Study (EOS)	The end of study is defined for a subject as either the date of death or the date when the long term follow-up period ends (i.e., when 2700 deaths have occurred) or early study termination , whichever comes first. For subjects lost to follow-up, this will be the date of last contact

Abbreviation or Term	Definition/Explanation
End of Treatment Period	The treatment period ends at the end of treatment period visit which is scheduled to occur at the next Q3W visit following disease progression. Subjects who are unable to continue Q3W visits and Q9W imaging studies until progression should complete EOTP procedures no later than their next Q3W visit (± 6 days). The date captured on the end of treatment period electronic case report form (eCRF) will not be used in determining time to disease progression; time to disease progression will be derived from the dates of imaging studies.
EOETP	End of the Efficacy Treatment Period
EOI	Event of Interest
EOS	End of Study
EOTP	End of Treatment Period
ESA	Erythropoiesis stimulating agent
First-line chemotherapy	Initial (first) chemotherapy given for a disease.
g/dL	Gram per deciliter
IBG	Independent Biostatistics Group. This group provides statistical support to a data monitoring committee (DMC) but is not a voting member of the DMC.
IP	Investigational Product
IVRS	Interactive Voice Response System
Kg	Kilogram
LTFU	Long term follow-up
MedDRA	Medical Dictionary for Regulatory Activities
hð	Microgram
моі	Medication of Interest
NSCLC	Non-small cell lung cancer
ORR	Objective (tumor) response rate
OS	Overall survival

Abbreviation or Term	Definition/Explanation
PFS	Progression-free survival
Pre-chemotherapy" Hemoglobin	The hemoglobin value taken just prior to the start of first- line chemotherapy for NSCLC
Q3W	Once-every-3-weeks
Randomization Day	This is the day subjects are randomized (enrolled) into the study through the interactive voice response system (IVRS). The randomization day may occur on the same day as the first dose of investigational product or it may occur up to 4 days before the first dose of investigational product.
RBC	Red blood cell
RECIST	Response evaluation criteria in solid tumors
SAE	Serious adverse event
Screening Hemoglobin	The local laboratory hemoglobin value obtained within 7 days prior to randomization; this is used to confirm eligibility and randomization stratum and will be used as a stratification factor for overall survival, progression-free survival, and incidence of transfusions from weeks 5 (ie, day 29) to end of treatment
Study Day 1.	This is the first day of investigational product administration. All laboratory assessments on study day 1 are to be completed before study drug administration and will be used as baseline measurements. The randomization day may occur on the same day as the first dose of investigational product or it may occur up to 4 days before the first dose of investigational product
Study Entry Hemoglobin	The hemoglobin value obtained closest to the date when the subject signs and dates the informed consent form (ICF). This may be a central or local laboratory hemoglobin value.

Abbreviation or Term	Definition/Explanation
Study Termination Date	The planned study termination date will be the date when the 2700 th death is reported in the clinical trial database or at an early termination date, if applicable . Once this death is reported or the early termination date is reached, sites will be instructed to enter all outstanding data into the clinical trial database, the database will be cleaned, a snapshot will be taken, the database will be locked, and the primary analysis will be performed. Any additional deaths reported during the entry of outstanding data which occur on or prior to the termination date will be counted in the primary analysis.
Study Week 1	The 7-day period beginning with study day 1 is considered study week 1.
Treatment Period	The treatment period begins on study day 1 and ends at the next Q3W visit following disease progression. Subjects who are unable to continue Q3W visits and Q9W imaging studies until progression should complete EOTP procedures no later than their next Q3W visit (± 6 days).
TVE	Thrombovascular event
VTE	Venous thromboembolic event

1. Introduction

The purpose of this Statistical Analysis Plan (SAP) is to provide details of the statistical analyses that have been outlined within the protocol for study 20070782, darbepoetin alfa dated 14 September 2017. The scope of this plan includes the **planned final** analysis and will be executed by the Amgen Global Biostatistics department unless otherwise specified.

This SAP does not cover the planned interim analyses; these are outlined in the Data Monitoring Committee charter and maintained by the Independent Biostatistics Group (IBG; PRA Health Sciences, Charlottesville, Virginia). The SAP also does not cover the unplanned interim analysis performed in Q4 2016.

The SAP was amended on 30 June 2017 to reflect a recommendation by the independent Data Monitoring Committee to terminate the study early and incorporates the current SAP Template and Tables, Figures, and Listing guidance.

2. Objectives, Endpoints and Hypotheses

2.1 Objectives and Endpoints

Objectives	Endpoints
Primary	
• To demonstrate non-inferiority of overall survival (OS) when comparing subjects on darbepoetin alfa treated to a hemoglobin ceiling of 12.0 g/dL to subjects treated with placebo	Overall survival
Secondary	
 To demonstrate non-inferiority of progression-free survival (PFS) when comparing subjects on darbepoetin alfa treated to a hemoglobin ceiling of 12.0 g/dL to subjects treated with placebo 	 Progression-free survival
• To demonstrate superiority in reducing the incidence of red blood cell (RBC) transfusions when comparing subjects on darbepoetin alfa treated to a hemoglobin ceiling of 12.0 g/dL to subjects treated with placebo	 Incidence of at least 1 RBC transfusion or hemoglobin ≤ 8.0 g/dL from week 5 (day 29) to end of the efficacy treatment period (EOETP; defined as 21 days after either the last dose of IP or the last dose of chemotherapy, whichever is later; the EOETP will be set to the EOTP if the EOETP exceeds the EOTP)
• If non-inferiority hypotheses are confirmed for both OS and PFS and the superiority hypothesis is confirmed for the transfusion endpoint, a superiority hypothesis will then be tested for both OS and PFS.	Overall all and progression-free survival
Other Endpoints	
• To assess other safety and efficacy parameters in subjects on darbepoetin alfa treated to a hemoglobin ceiling of 12.0 g/dL compared to subjects treated with placebo	 Incidence of adverse events such as thrombovascular events (TVE), venous thromboembolic events (VTE), and AEs associated with RBC transfusions Objective tumor response rate Incidence of neutralizing antibody formation to darbepoetin alfa

 Incidence of at least 1 RBC transfusion or hemoglobin ≤ 8.0 g/dL from study day 1 to EOETP
Change in hemoglobin from baseline to EOETP

2.2 Hypotheses and/or Estimations

The primary hypothesis to be tested is that the OS of subjects treated with darbepoetin alfa is not worse than the OS of subjects treated with placebo. The hypothesis for OS will be confirmed if the upper confidence limit for the hazard ratio (darbepoetin alfa to placebo) is less than 1.15 using a 1-sided significance level of 0.025.

If the primary hypothesis is confirmed, the secondary hypothesis that PFS is not worse in subjects treated with darbepoetin alfa than the PFS in subjects treated with placebo will be tested. The hypothesis for PFS will be confirmed if the upper confidence limit for the hazard ratio is less than 1.15 using a 1-sided significance level of 0.025.

If both the OS and PFS hypotheses are confirmed, the hypothesis that the incidence of RBC transfusions is less in subjects treated with darbepoetin alfa than in subjects treated with placebo will be tested. This hypothesis will be confirmed if the p-value is < 0.05 from a two-sided Cochran-Mantel-Haenszel test comparing darbepoetin alfa to placebo with respect to the incidence of at least 1 RBC transfusion or hemoglobin \leq 8.0 g/dL from day 29 to EOETP.

If non-inferiority hypotheses are confirmed for both OS and PFS and the superiority hypothesis is confirmed for the transfusion endpoint, a superiority hypothesis will then be tested for both OS and PFS. These hypotheses will be confirmed by examining the p-values associated with hazard ratios from both OS and PFS; the Hochberg procedure will adjust for multiplicity and maintain an overall two-sided significance level of 0.05.

3. Study Overview

3.1 Study Design

This is a double-blind, randomized, placebo-controlled, phase 3 study in CIA subjects receiving multi-cycle chemotherapy for the treatment of advanced stage NSCLC cancer. Randomization will occur in a 2 to 1 ratio (darbepoetin alfa to placebo) and will be stratified by histology (squamous versus other), screening hemoglobin (< 10.0 g/dL versus \geq 10.0 g/dL), and geographic region (see Section 4.1 for regions).

Subjects will receive IP Q3W during the treatment period. IP will be discontinued within 3 weeks after the completion of chemotherapy, or upon the determination of disease progression, whichever occurs first. Study visits Q3W and imaging studies Q9W will occur during the treatment period until disease progression.

An end of the treatment period visit will occur at the next Q3W visit after disease progression has been determined. **Hemoglobin and other hematology and chemistry values collected beyond this period (ie, beyond 3 weeks after disease progression) will be excluded from analysis.** Subjects will then enter long term follow-up and will be followed for survival until death, until approximately 2700 deaths have occurred **or until early study termination**.

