7.1.6 Imaging Studies

Subjects must have had a pre-chemotherapy scan (computed tomography [CT], magnetic resonance imaging [MRI] or positron emission tomography-computer tomography [PET/CT with diagnostic quality CT]) of the chest to assess disease burden at baseline. The scan must include the chest and is expected to include the adrenal glands. The scan(s) must be reviewed by the investigator prior to randomization. If the scan was performed more than 28 days prior to randomization, an additional scan must be performed and reviewed by the investigator to confirm that the patient has not

progressed before randomization. Subjects who have progressed are not eligible for randomization.

Throughout the study, a subject will be followed by the same method of assessment that was used at baseline to ensure consistency and comparability of images. When possible, similar scanning techniques and equipment, including level and thickness should be used as at baseline for a subject. Tumor assessments will be performed according to the modified RECIST 1.1 criteria (Appendix H) and must be conducted according to protocol specified techniques.

After randomization, imaging studies will be performed every 9 weeks (± 7 days) from study day 1/week 1 or sooner if clinically indicated until disease progression as defined by modified RECIST 1.1 criteria. Once disease progression has been determined, imaging studies are no longer required.

Additional CT scans of other body regions (eg, brain, bone) may be acquired in the event of a suspected metastasis as clinically appropriate for evaluation and management. If there are signs or symptoms suggestive of bone metastasis, a bone scan, MRI, CT, PET, PET/CT, or X-ray will be performed. For subjects with a positive bone scan or PET scan, the bone metastasis must be confirmed with another method of imaging (ie, X-ray, CT or MRI). Evidence of suspected disease progression must be recorded in source documents at the site.

Images from the imaging studies will be collected and stored in a central location by the imaging vendor. Refer to the imaging manual for additional information and instructions on the handling and shipping of the images to the imaging vendor.

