7.6 End of Treatment Period

Subjects will complete the EOTP visit at the next Q3W visit (± 6 days) after disease progression has been determined either by imaging studies or by clinical assessments in the absence of imaging confirmation. Subjects who are unable to continue Q3W visits and Q9W imaging studies until disease progression should complete EOTP procedures

at no later than their next Q3W visit (\pm 6 days). At the time of the EOTP visit, any subject who has experienced a serious and treatment related adverse event during the study, as determined by the investigator, will continue to be followed for that event, until the event is resolved or considered stable; all EOTP visit procedures may still be conducted prior to resolution.

The following EOTP assessments and procedures will be required for all subjects:

- Vital signs and weight
- The presence of a central or mid-line venous catheter
- ECOG performance status
- Assess for signs and symptoms of clinically relevant TVE. If present, perform appropriate laboratory, diagnostic, and medical imaging for suspected TVE
- Adverse events, concomitant medications, radiotherapy, anti-cancer therapy, anticancer surgery, and RBC transfusions
- Central laboratory serum chemistries and CBC with differential (including hemoglobin for statistical analyses) (except if EOTP visit occurs following the Q3W visit after the last dose of IP)
- Local laboratory hemoglobin (except if EOTP visit occurs following the Q3W visit after the last dose of IP)
- Darbepoetin alfa antibody

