period. This will be summarized both by keeping a 21-day window after each RBC transfusion and **excluding** a 21-day window after each RBC transfusion.

RBC transfusion or hemoglobin ≤8.0 g/dL from week 5 (day 29) to EOETP

Any RBC transfusion (packed RBCs or whole blood) given or a hemoglobin ≤8.0 g/dL on or after study day 29 until the EOETP, inclusive.

RBC transfusion or hemoglobin ≤8.0 g/dL from week 1 (day 1) to EOETP

Any RBC transfusion (packed RBCs or whole blood) given or a hemoglobin ≤ 8.0 g/dL on or after study day 1 until the EOETP, inclusive.

RBC transfusion from week 5 (Day 29) to EOETP

Any RBC transfusion (packed RBCs or whole blood) given on or after study day 29 until the EOETP, inclusive.

RBC transfusion from week 1 (Day 1) to EOETP

Any RBC transfusion (packed RBCs or whole blood) given on or after study day 1 until the EOETP, inclusive.

Thrombovascular event (TVE)

Thrombovascular events are adverse events that include arterial thromboembolic events (ATEs), venous thromboembolic events (VTEs), and unspecified/mixed thromboembolic events. These events will be coded using MedDRA version **20.0** (or higher) and identified using a Standardized MedDRA Query (SMQ 2000081, "embolic and thrombotic events") or more appropriate query available at the time of analysis. **Arterial thromboembolic event (**ATEs**)**, **Venous thromboembolic event (**VTEs**) and Unspecified/mixed thromboembolic events** are described below:

• ATE

ATEs include stroke, transient ischemic attack (TIA), acute coronary syndromes (ACS), and other arterial thrombosis/embolism. These events will be coded using MedDRA version **20.0** (or higher) and identified using the sub-SMQ 20000082 ("embolic and thrombotic events, arterial") or more appropriate query available at the time of analysis.

• VTE

VTEs include deep vein thrombosis (DVT), pulmonary embolism (PE), and other venous thrombosis excluding superficial venous thrombosis. These events will be coded using MedDRA version **20.0** (or higher) and identified using the sub-SMQ 20000084 ("embolic and thrombotic events, venus") or more appropriate query available at the time of analysis. In

addition, VTEs will be distinguished by whether or not they were confirmed by imaging. The primary analysis of VTEs will include fatal VTEs and VTEs confirmed by imaging; a sensitivity analysis will summarize all VTEs regardless of severity or confirmation.

Unspecified/mixed thromboembolic event

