	Imaging studies will be performed every 9 weeks (± 7 days) or at any time symptoms suggestive of disease progression occur. Subjects who discontinue chemotherapy or IP should continue to be evaluated radiographically Q9W until disease progression.	Every 8-10 weeks until progression
EOTP	The EOTP visit is the next Q3W visit (± 6 days) after disease progression	n/d
Long-term follow-up (LTFU)	 LTFU begins after disease progression. Visits should occur at 3-month intervals (± 2 weeks). and	n/d
EOS	EOS is when a subject dies or is lost to follow- up or withdrawal or until 22 June 2017	n/d

n/d Not determinable – since many of these are event driven, the period for an individual subject cannot be determined apriori

Additional description of per protocol analysis

• Exclude subjects with EN 111 or EN 101 or OT 903

This excludes:

a) subjects that did not have NSCLC (OT 903)

b) subjects that did not have metastatic (Stage IV) or advanced stage IIIB with malignant pleural effusion NSCLC (prior to Amendment 3) (ie, subjects that had a lower grade tumor)

• Exclude subjects with EN 117A

This excludes subjects with disease progression prior to study day 1

• Exclude subjects with EN 202

This excludes subjects with a history of or current cancer diagnosis of a cancer type other than NSCLC

• Exclude subjects with EN 109 or EN 117 B

This excludes subject who did not have a baseline pre-chemo scan prior to randomization

- Exclude subjects with an ECOG performance status > 1 at screening (EN 113 or EN 103)
- Exclude subjects with EN 114 or EN 105

This should exclude subjects that had a life expectancy < 6 months based on the judgment of the investigator at screening

- Exclude subjects who received any erythropoiesis stimulating agents within the 28 days prior to screening (EN 223 or 218)
- Exclude subjects with EN 210 This should exclude subjects with a documented history of pure red cell aplasia
- Exclude subjects who are not dosed per protocol through week 7 (however, include subjects who received a planned dose adjustment per section 6.1.2 of the protocol)
- Exclude subjects who did not receive first line chemotherapy with an initial start date on or before Study day 1 and an end date after Study day 1

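### SAP 3.1 ends the laboratory window in two ways that disagree: at the EOTP visit, and at 3 weeks after progression

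*SAP*

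**What the plan says.** SAP 3.1 first fixes the end of the treatment period: "An end of the treatment period visit will occur at the next Q3W visit after disease progression has been determined". The next sentence provides that hemoglobin, other hematology and chemistry "values collected beyond this period (ie, beyond 3 weeks after disease progression) will be excluded from analysis".

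Other places define the same period by the visit, with no fixed number of days:

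- Protocol 7.6: "Subjects will complete the EOTP visit at the next Q3W visit (± 6 days) after disease progression has been determined".
- SAP Appendix A, EOTP row of the visit table: "The EOTP visit is the next Q3W visit (± 6 days) after disease progression".
- SAP list of definitions, Treatment Period: "The treatment period begins on study day 1 and ends at the next Q3W visit following disease progression".

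Three further provisions decide what the cut-off touches:

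- The SAP definition of End of Treatment Period says that "time to disease progression will be derived from the dates of imaging studies". Protocol 7.1.6 allows each Q9W scan ±7 days.
- SAP section 5 counts a transfusion or a hemoglobin ≤ 8.0 g/dL "on or after study day 29 until the EOETP, inclusive". EOETP is 21 days after the later of the last IP and last chemotherapy dose, capped at EOTP.
- Protocol 7.6 and footnote o of protocol Appendix A omit the EOTP chemistry, CBC and local hemoglobin if EOTP comes later than the first Q3W visit after the last IP dose.

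**The concern.** The parenthesis in SAP 3.1 treats the EOTP visit and day 21 after progression as the same date. They coincide only at nominal timing. A programmer could implement either half of the sentence, and the two filters give different data sets.

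With the 21-day filter, values taken inside the permitted visit window are lost from the SAP 9.6.5 summaries of EOTP and of change to EOTP. They are also lost from the count of hemoglobin > 12 g/dL, which SAP section 5 assesses over the whole treatment period. The exclusion covers laboratory values and not transfusions, so the two components of the secondary composite could stop on different dates. That composite is formally tested and must succeed before superiority of OS and PFS is tested. Subjects who complete EOTP without progressing have no progression date, so the 3-week limit cannot be applied to them at all.

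**Working it through.** **Inputs.** Q3W interval 21 days; EOTP window ±6 days (protocol 7.6, SAP Appendix A); scan window ±7 days (protocol 7.1.6); EOETP = min(last IP or chemotherapy dose + 21, EOTP) (SAP definitions). Day 0 is the nominal day of the last dosing visit, and the EOTP visit is nominally day 21. A sample is excluded if its gap from progression exceeds 21 days.

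**Step 1: the plan's own figure.** Progression determined on day 0 after dosing, EOTP on day 21: gap 21 − 0 = 21. The 3 weeks reproduces, and the sample is kept.

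**Step 2: use the permitted windows.**

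| Case | Progression dated | EOTP sample | Gap (days) |
|---|---|---|---|
| EOTP 6 days late, nothing else moved | 0 | 27 | 27 |
| Scan 7 days before the dosing visit, read after the dose, EOTP on time | −7 | 21 | 28 |
| Dosing visit 6 days early, EOTP 6 days late, dated by determination | −6 | 27 | 33 |
| Early scan read after the dose, and EOTP 6 days late | −7 | 27 | 34 |

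All four exceed 21. The first needs only the stated EOTP window. It is a limiting case: progression must be determined on the dosing day but after the dose. Each day that determination comes later shortens the gap by one day.

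**Step 3: when is a sample scheduled?** Under footnote o, laboratory tests are done at EOTP only if the last IP dose was at the visit just before it. If progression is determined before dosing at a visit, IP stops, the last dose was one visit earlier, and the next visit has no scheduled sample to lose.

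**Step 4: when is the composite touched?** Let b be the EOTP sample day, p the progression date and L the later of the last IP and last chemotherapy dose.

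- Excluded by the 3-week limit: b − p > 21, so p < b − 21.
- Inside the endpoint window: b ≤ L + 21, so b − 21 ≤ L.

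Both hold only if p < L, that is, if a dose was given after the progression date. With scan dating this happens whenever a dose falls between the scan and its reading. With determination dating it needs chemotherapy after progression was determined, because IP stops at that point.

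**Step 5: example in study days, visits on time.** Scan on day 58 (within 7 days of day 64), IP and chemotherapy on day 64, progression read on day 66, EOTP on day 85.

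- EOETP = min(64 + 21, 85) = day 85, so a hemoglobin ≤ 8.0 g/dL on day 85 is an endpoint event.
- From the scan: 85 − 58 = 27 days, excluded.
- From determination: 85 − 66 = 19 days, kept.

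A transfusion on day 85 counts either way.

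**Step 6: a case that spares the composite.** Last IP and chemotherapy on day 0, progression dated day 0, EOTP on day 27. EOETP = min(21, 27) = day 21. The day-27 hemoglobin is already outside the endpoint window, and only the laboratory summaries lose it.

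**The case against.** The best defence is that the operative words point to the treatment period, and the 3 weeks merely paraphrases Q3W. On that reading every EOTP sample is kept, in line with SAP 9.6.5 and Appendix A. This may well be what was intended. It does not rescue the sentence, because the parenthesis gives a numeric limit that contradicts the intention and could be programmed as written.

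It can also be said that SAP 3.1 speaks of progression being determined, and that the scan-date sentence governs time to progression, not laboratory windows. That is fair, and it is why the effect on the composite is conditional: the example in step 5 is kept if counted from determination. The EOTP window still produces 27 days without any scan date.

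A reader might infer that most progressors lose their last sample. Take scans uniform over 0 to 7 days before the dosing visit and EOTP uniform over ±6 days. Then 76 of 8 × 13 = 104 combinations (73%) exceed 21 days, and with EOTP exactly on time 7 of 8 (88%) do. These figures assume that every scan is read only after the next dose. A scan read earlier makes that visit itself the EOTP. Add an assumed uniform reading lag, with a reading on the visit day taken to precede dosing. The share exceeding 21 days from the scan falls to 40/416 (10%) for a lag of 0 to 3 days and 224/832 (27%) for 0 to 7 days. Even in the 104-cell grid, only 28 (27%) also lie on or before EOETP when the last IP and chemotherapy were at the dosing visit. The documents give no reading lag, so none of these shares is an estimate for this trial.

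Some mitigation is planned. SAP 9.5.2 includes a transfusion-only analysis, and change in hemoglobin falls back to the last available value and is also reported at weeks 13 and 16.

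**Conclusion.** Wrong as written, minor severity. The numeric limit in SAP 3.1 conflicts with the SAP's own EOTP window by up to 6 days (27 against 21) with visits otherwise on schedule, and by more if progression is dated by an earlier scan. Literal use drops scheduled EOTP laboratory values in subjects last dosed at the preceding visit. It reaches the secondary composite only where a dose was given after the date used for progression, which mainly means scan dating.

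Three stronger conclusions are not supported:

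- A gap of 34 days (7 + 21 + 6) is a stacked case stated in neither document. It is not a ceiling either, since protocol Appendix H back-dates equivocal progression to the earlier suspicion.
- The number of subjects affected cannot be computed from the documents.
- Dilution of the treatment difference through more lost events on placebo is conjecture. An event is lost only if the excluded hemoglobin is ≤ 8.0 g/dL and is that subject's sole qualifying event since day 29.

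OS and PFS are unaffected.

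**What to change.** In SAP 3.1, delete the 3-week parenthesis and state that hemoglobin, hematology and chemistry values collected after the actual EOTP visit date are excluded. Because EOETP is already capped at EOTP, all values through EOETP then remain available for the transfusion-or-hemoglobin endpoints without a further rule. The cut-off also no longer depends on whether progression means the scan date or the determination date, and it works for subjects who reach EOTP without progressing.

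The cost is one SAP sentence and one programming filter, with no new data. It should be settled before the database is locked.
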